### **Software**

All analyses will be performed using Statistical Analysis System (SAS)® Software version 9.4 or higher.

## **10 Study Patients**

The subsections in this section include specifications for reporting patient disposition and study dose/study discontinuations. Additionally, procedures for reporting protocol deviations are provided.

### **10.1 Disposition of Patients and Discontinuations**

This section describes how patient disposition, and study and study dose discontinuations will be summarized. The following disposition categories will be considered.

- Total number of screened patients
- Number of enrolled patients (i.e., those who gave informed consent and met all the entry criteria). The corresponding percentage will be calculated using the number of screened patients as a denominator.

For the following categories, the corresponding percentage will be calculated with respect to the number of enrolled patients:

- Number of patients who received at least one dose of the study treatment
- Number of patients who completed the 24-month study
- Number of patients who discontinued the study treatment, grouped by main reasons (reason from last study dose stopped). The percentages for the reasons will be calculated using the number of patients who discontinued the study treatment as the denominator.
- Number of patients who discontinued the 24-month study, grouped by main reasons. The percentages for the reasons will be calculated using the number of patients who discontinued the study as the denominator.

## **10.2                    Protocol Deviations**

Analysis of protocol deviations will be performed on the FAS, unless otherwise stated. Protocol deviations will be collected in a deviation log.

### **10.2.1                Important Protocol Deviations**

The following summary table of important protocol deviations will be provided:

- Frequency table per reason of important protocol deviations

### **10.2.2                Reasons Leading to the Exclusion from an Analysis Population**

For patients excluded from the PP, the reasons for exclusion will be summarized and listed:

- Frequency table per reason of exclusion from the PP population
- Listing of reasons for exclusion from the PP population (The listing will include the patient ID and the reason for exclusion from the PP Analysis Set.)

## **11                    Demographics and Other Baseline Characteristics**

If not stated otherwise, summaries will be presented for the FAS and PP populations. Missing values for the Baseline characteristics will be treated as described in Section 9, unless otherwise stated.

### **11.1                Demographics**

Demographic characteristics will be summarized using the following information from the demographics eCRF pages:

- Demographic characteristics
  - Sex: Male, female

- Race: White, Black or African American, Asian, Native Hawaiian or other Pacific Islander, American Indian or Alaska Native, other
- Ethnicity: Hispanic or Latino, Not Hispanic or Latino, Not reported, Unknown
- Age (years)
- Age categories:
  - <65 years,
  - $\geq 65$  years
  - 65-74, 75-84,  $\geq 85$
- Weight

Specifications for computation:

- Age [years]
  - $(\text{date of informed consent} - \text{date of birth} + 1) / 365.25$

## **11.2                    Medical History**

The medical history will be summarized from the “Medical History” eCRF page, using the Medical Dictionary for Regulatory Activities (MedDRA), current version, and preferred term (PT) as an event category and system organ class (SOC) body term as Body System category.

Medical history will be displayed in terms of frequency tables ordered by primary SOC and PT in alphabetical order.

It is recommended to use the most current MedDRA version at the time of data cutoff.

## **11.3                    Other Baseline Characteristics**

Summary statistics will be presented for:

- Elapsed time since diagnosis of MS (years)
- Proportion of patients with MS diagnosis  $< 24$  months ( $\geq 24$  months) before study
- Elapsed time since first symptoms of MS (years)
- Baseline PRO data
- Baseline laboratory data
- Baseline data on previous MS DMD use
- Relapses during the previous 2 years (1 year, if MS diagnosis is  $< 24$  months)
- ARR (retrospective data)
- Baseline MRI data

- MRI data in the 2 years prior to study enrollment or since MS diagnosis, if diagnosis <24 months
- Past treatment adherence (collected via ePRO: MS-TAQ modified version for once- or twice-daily oral dosing to assess adherence during last previous oral DMD treatment and MS-TAQ version modified to assess adherence during last previous infused DMD treatment)
- Pregnancy and comorbid conditions (human immunodeficiency virus [HIV], hepatitis B, hepatitis C, tuberculosis, and CCI [REDACTED])

### Elapsed Time Since Diagnosis of MS

Elapsed time since the diagnosis of MS will be calculated as:

$$\text{Elapsed time since diagnosis of MS (days)} = \text{Informed consent date} - \text{Initial MS diagnosis date}$$

$$\text{Elapsed time since diagnosis of MS (months)} = (\text{Informed consent date} - \text{Initial MS diagnosis date})/30.4375$$

$$\text{Elapsed time since diagnosis of MS (years)} = (\text{Informed consent date} - \text{Initial MS diagnosis date})/365.25$$

It will be summarized descriptively as a continuous variable.

### Elapsed Time Since First Symptoms of MS

Elapsed time since the first symptoms of MS will be calculated as:

$$\text{Elapsed time since first symptoms of MS (days)} = \text{Informed consent date} - \text{First attack date}$$

$$\text{Elapsed time since first symptoms of MS (months)} = (\text{Informed consent date} - \text{First attack date})/30.4375$$

$$\text{Elapsed time since first symptoms of MS (years)} = (\text{Informed consent date} - \text{First attack date})/365.25$$

It will be summarized descriptively as a continuous variable.

### Relapses During the Previous 2 Years

The number of relapses during the previous 2 years (or since MS diagnosis if <2 years) and the duration of these relapses will be summarized descriptively as continuous variables.

### **ARR (Retrospective Data)**

The ARR based on the last 24 months prior to the start of treatment with cladribine tablets will be assessed. The retrospective 24-month ARR for a patient is calculated as:

*(No. of relapses within 24 months prior to written informed consent for that patient / [30.4375\*24]) \* 365.25*

For patients diagnosed with MS at least 12 months but less than 24 months prior to written informed consent, the number of relapses since MS diagnosis will be used, and the ARR calculation will be as follows:

*(No. of relapses since MS diagnosis and prior to written informed consent for that patient / [Informed consent date - Initial MS diagnosis date]) \* 365.25*

Such a variable will be summarized descriptively.

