- Treatment adherence questions, based on modified versions of the Multiple Sclerosis Treatment Adherence Questionnaire (MS-TAQ); data to be collected via ePRO at baseline (modified for once or twice daily oral dosing to assess adherence during last previous oral DMD treatment or modified for infusion dosing to assess adherence to last previous infusion DMD treatment) and at the end of Months 1, 2, 13, and 14 (modified for cladribine tablets); a Spanish translation is available to patients.
- Proportion of patients experiencing a relapse. For this study, a relapse will be defined as determined and recorded by the investigator and information on the definition used by the investigator will be collected (see Section 9.1.2.1 for a guide on definition).
- Proportion of patients with relapse associated with hospitalization (relapse as primary diagnosis or reason for hospitalization). For this study, a relapse will be defined as determined by the investigator (see Section 9.1.2.1 for a guide on definition).
- Proportion of patients with relapse associated with glucocorticoid use. For this study, a relapse will be defined as determined by the investigator (see Section 9.1.2.1 for a guide on definition).
- Assessment of previous treatment for MS:
 - Previous DMD(s) received for MS prior to study enrollment, since MS diagnosis
 - Reasons for discontinuation of previous DMD(s)
- Assessment of clinical and demographic characteristics of patients who switch from ocrelizumab to oral cladribine tablets
 - Reasons for discontinuation of ocrelizumab
- Proportion of patients who discontinue oral cladribine tablets
 - Reason for discontinuation of cladribine tablets
 - Elapsed time to discontinuation after first dose
 - Number of doses and % of planned doses (as per USPI) received
 - Subsequent treatment chosen following discontinuation of cladribine tablets
- Assessment of concomitant MS medications used during study period
- The ARR based on the last 24 months (or since MS diagnosis, if diagnosis <24 months) prior to the start of treatment with cladribine tablets (retrospective data). For this study, a relapse will be defined as determined by the investigator (see Section 9.1.2.1 for a guide on definition).

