9.2.4 Frequency of Assessments

Table 1 lists the Schedule of Assessments. Patients are considered enrolled once the informed consent form (ICF) has been signed prior to any data collection for this study. The Baseline Visit is the visit immediately prior to the patient initiating treatment with cladribine tablets. If the sites anticipate a delay between the decision to start cladribine tablets and patient access to cladribine

tablets (i.e. due to delays in cladribine tablets availability or access), the site can perform a Screening Visit first to determine eligibility of the patient and a subsequent Baseline Visit closer to the time the patient starts taking cladribine tablets. Data entered during the Baseline Visit are considered baseline data for the purposes of analysis.

Sites are asked to enter patient follow-up data for up to 24 months after a patient received the initial month dose of cladribine tablets if Year 2 treatment course is not delayed, and up to 30 months after initial dose if Year-2 treatment course is delayed up to 6 months. Visits will be conducted within the context of routine clinical care; thus, the timing of study visits is approximate and not mandated by the study protocol.

It is anticipated that patients enrolled in the study may not immediately start cladribine tablets after the decision to initiate cladribine tablets is made, owing to the need to first discontinue their current oral or infusion DMD (for a time period determined by the investigator) and to potential delays in obtaining cladribine tablets in the clinical setting. The initial PRO only collection (Month 1) is intended to be obtained after the patient has started treatment with cladribine tablets. The timing of Visit 1 (Month 2) and the subsequent visits may need to be adjusted based upon the actual start date of cladribine tablets, which will be recorded by the investigator.

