Treatment patterns: Prior treatment patterns will be described at baseline (previous DMD treatment(s) and baseline characteristics of patients initiating cladribine tablets). Treatment discontinuation of cladribine tablets and the reasons for discontinuation will be described, as will be the follow-up treatments.

Annualized Relapse Rate (retrospective assessment): The ARR during the last 24 months before starting cladribine tablets (or since MS diagnosis, if diagnosis <24 months) will be presented, accompanied by the respective 95% CIs.

CCI

CCI

Safety: All safety data (AEs and hematology data, including lymphocyte subtype data, as available) will be evaluated descriptively.

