To estimate the ARR over the 24-month period prior to initiation of cladribine tablets (or since MS diagnosis if diagnosis <24 months)	The ARR based on the last 24 months prior to the start of treatment with cladribine tablets (or since MS diagnosis if diagnosis <24 months) (retrospective data)	24-month period prior to initiation of cladribine tablets (or since MS diagnosis if diagnosis <24 months)	Section 11.3
To collect all Serious Adverse Events (SAEs), Adverse Drug Reactions (ADRs), Adverse Events of Special Interest (AESIs), and special situations during treatment with cladribine tablets over a 24-month period	SAEs, ADRs, AESIs	Adverse event (AE) collected from signed Informed Consent Form; Treatment-Emergent Adverse Events (TEAEs) considered after first treatment administration through the 24-month treatment period (or 30 months if Year 2 treatment is delayed)	Section 15

CCI

## 6

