### Subgroups:

The following subgroups will be defined:

- Patients completing the 24-month study
- Patients not completing the 24-month study (i.e., lost to follow-up, withdrawing consent, protocol deviations)
- Patients not completing the treatment (i.e., completing Year 1 treatment but not Year 2 treatment, or not completing both courses of treatment each year)
- Type of MS at screening: RRMS, aSPMS, PPMS, CIS
- Patients diagnosed with MS <24 months before transitioning to cladribine tablets
- Centers
  - Pooling of centers: Because of the high number of participating centers and the anticipated small number of patients in each center, data will be pooled across centers,

and the factor centers will not be considered in statistical models or for subgroup analyses.

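### SAP 11.3 computes the retrospective relapse rate up to informed consent, although the outcome is defined up to the start of cladribine

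*SAP*

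**What the plan says.** **Definition.** SAP Section 5 gives the objective as "To estimate the ARR over the 24-month period prior to initiation of cladribine tablets", with time since diagnosis used instead when that is under 24 months. Protocol 8.2 and 9.1.2.2 end the window at the same point, and Protocol 9.7.3 describes the analysis as "The ARR during the last 24 months before starting cladribine tablets". SAP 11.3, under ARR (Retrospective Data), opens the same way: "The ARR based on the last 24 months prior to the start of treatment with cladribine tablets will be assessed".

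**Formulas.** The first formula under that sentence counts "No. of relapses within 24 months prior to written informed consent for that patient" and divides by 30.4375 × 24 days. The second, for diagnoses at least 12 but less than 24 months before consent, counts "No. of relapses since MS diagnosis and prior to written informed consent for that patient" and divides by the days from diagnosis to consent.

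**Timing.** Protocol 9.2.4 treats a patient as enrolled at signature of the consent form. Table 1 places consent at the pre-baseline Screening Visit, Days -60 to 0. A separate visit is optional: if a delay is expected, "the site can perform a Screening Visit first to determine eligibility of the patient". The same section foresees delay while the previous drug is stopped and cladribine is obtained. SAP 14.1.1 starts prospective time on study at first dose.

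**Related relapse counts.** SAP 11.3 also summarizes relapses in the previous 2 years. For recent diagnoses its list of characteristics says 1 year, while the definition further down says since diagnosis. No reference date is given. The same count, cut at ≤1 versus >1, is the covariate in the negative binomial models (SAP 14.1.1 and 14.1.2), and the count is an imputation variable in SAP 14.1.4.

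**Previous disease-modifying drugs (DMDs).** Protocol 9.1.2.2 and 9.3 cover DMDs and reasons for stopping them since diagnosis, and the SAP Section 5 objective has the same scope. The SAP Section 5 endpoint row and the listing, by-drug and reasons tables in SAP 11.3 are limited to the last 2 years. The endpoint row restricts reasons to the last previous DMD.

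**The concern.** A programmer works from the formula, not from the sentence above it. Coded as written, the SAP produces a secondary outcome that differs from the one in the protocol and in its own objectives table.

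The omitted interval is not arbitrary. It runs from consent to first dose, when patients may be coming off their previous drug, so a relapse rate equal to that of the preceding two years is an assumption. Because prospective follow-up starts at first dose, the interval belongs to neither ARR.

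The rule that selects the formula, less than 24 months since diagnosis, is also judged at consent. The subgroup in SAP 8.2 uses the same cut-off but counts "months before transitioning to cladribine tablets". A patient near the cut-off could fall on different sides in the two places.

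**Working it through.** The documents state no result to reproduce, so the check sets the definitions side by side and then sizes the gap.

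**Inputs.** One month is 30.4375 days and one year 365.25 days (SAP Section 9). The gap g from consent to first dose is not given. I use 0, 30, 45 and 60 days. Sixty days is the longest planned Screening-to-Baseline interval (Protocol Table 1). Forty-five days was the limit from August 2019 to July 2022, according to the amendment log.

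**Window length.** 30.4375 × 24 = 730.5 days. One relapse therefore adds 365.25 / 730.5 = 0.5 to a patient's ARR under the first formula.

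**Share affected.** For the 24-month window, the displaced share is g / 730.5. For a patient diagnosed 365.25 days before consent, the omitted share is g / (365.25 + g). Patients switch formula if diagnosed between (730.5 − g) / 30.4375 and 24 months before consent.

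| Gap (days) | 24-month window displaced | 12-month case omitted | Switching band starts (months) |
|---|---|---|---|
| 0 | 0% | 0% | none |
| 30 | 4.1% | 7.6% | 23.0 |
| 45 | 6.2% | 11.0% | 22.5 |
| 60 | 8.2% | 14.1% | 22.0 |

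**Effect on the mean.** Let k be the relapse rate in the gap divided by the rate in the rest of the window. The values 0.5, 1 and 2 are assumptions. The ARR ending at first dose, divided by the ARR ending at consent, is:

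- 24-month case: 1 + (k − 1) × g / 730.5
- 12-month case: (365.25 + k × g) / (365.25 + g)

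Inverting gives the SAP figure relative to the protocol figure:

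| Case, gap | k = 0.5 | k = 1 | k = 2 |
|---|---|---|---|
| 24-month, 30 days | +2.1% | 0% | −3.9% |
| 24-month, 60 days | +4.3% | 0% | −7.6% |
| 12-month, 30 days | +3.9% | 0% | −7.1% |
| 12-month, 60 days | +7.6% | 0% | −12.4% |

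At an assumed 0.5 relapses per year and a 60-day gap, the 24-month SAP figure of 0.500 compares with 0.479 (k = 0.5) or 0.541 (k = 2), a difference of +0.021 or −0.041.

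**Risk in re-anchoring.** If relapses in the gap were never recorded, moving the window to first dose adds event-free days. At a constant rate and a 60-day gap, the rate would be understated by 60 / 730.5 = 8.2%, or 60 / 425.25 = 14.1% in the 12-month case. Protocol 9.3 collects relapses for the two years before the study period without saying when that period starts, so capture has to be checked first.

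**The case against.** Consent is the SAP's usual reference date: age, time since diagnosis and time since first symptoms all use it. The formulas could therefore be a deliberate convention. Each matches its numerator to its denominator, so at a constant rate the mean is unbiased. The outcome is descriptive. SAP Section 7 is largely redacted and might declare the change.

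Much of this stands, and it limits the point. Protocol 9.3 itself ties MRI and DMD history to enrollment, which means consent, so the consent dates in SAP 11.3 for those two items are correct. A declaration in Section 7 cannot be ruled out. None of this removes the contradiction inside SAP 11.3, where the lead sentence and the formulas name different end dates.

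Four stronger readings are tempting, and the documents do not support them:

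- **The primary ARR is affected.** SAP Section 5 sets its timeframe from first dose, and its time on study starts there.
- **Sixty days is the most the gap can be.** Table 1 bounds Screening to Baseline only. Baseline to first dose is not bounded, and Protocol 9.2.4 calls visit timing approximate. Equally, the gap can be zero.
- **The two 24-month cut-offs corrupt a subgroup result.** SAP 14.1.4 details no analysis of the recently diagnosed, although the general sentence in SAP 8.2 covers every listed subgroup. SAP 8.2 also does not define transition as the first-dose date.
- **DMDs taken before the last 2 years go unreported.** The SAP also counts previous DMDs in total and summarizes DMDs since diagnosis for patients diagnosed 12 to less than 24 months before consent. Section 12, on previous medications, is redacted.

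**Conclusion.** The contradiction is real. Both retrospective ARR formulas end at consent, while the protocol, the SAP objectives table and the section's own lead sentence end at the start of cladribine.

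The size depends on a gap that the documents do not give. Over 0 to 60 days it displaces 0% to 8.2% of the 24-month window, and omits up to 14.1% for a patient diagnosed 12 months before consent. A longer delay would exceed these figures. A bias in the mean requires a different relapse rate in the gap, and its direction is unknown. The primary ARR formula is untouched. The unanchored 2-year count matters only where it is reused, in the negative binomial sensitivity models and the imputation model.

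The DMD mismatch is a narrower, secondary point: the visible endpoint row and tables do not match the scope of the objective they serve.

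**What to change.** **Check capture first.** Produce one listing of consent, Baseline and first-dose dates, with the onset date of every relapse in between.

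**If relapses in the gap were recorded:**
- End both formulas at the date of first dose. Apply this to the numerator, the denominator (first dose minus diagnosis in the second formula) and the 24-month rule that selects the formula.
- Use the same date for the 2-year relapse count in SAP 11.3 and for the covariate and imputation variable built on it in SAP 14.1.1, 14.1.2 and 14.1.4.
- In the SAP 11.3 list, replace 1 year with since diagnosis.
- Label the formula-selection flag separately from time since diagnosis, which stays at consent.

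**If they were not recorded:** keep consent as the end date, correct the lead sentence in SAP 11.3 and the row in SAP Section 5, and declare the change from the protocol unless the redacted Section 7 already does so.

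**Leave alone:** the consent anchor for MRI and DMD history in SAP 11.3, and the primary relapse count.

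**Previous DMDs:** extend the by-drug and reasons tables to all DMDs since diagnosis, align the SAP Section 5 endpoint row, and keep the 2-year table as a subset.

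**Cost:** one listing, SAP wording and reference-date programming. Relapse onset dates and DMD history since diagnosis are already among the variables in Protocol 9.3, so no new data collection is needed.

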### **Baseline PROs, Laboratory and MRI Data**

Baseline PROs, laboratory and MRI data are anticipated to be collected before the first dose of cladribine tablets is taken.

Baseline PROs and laboratory data will be summarized descriptively as continuous variables.

The most recent MRI prior to starting cladribine tablets (baseline MRI), which is expected to have been taken within the prior 90 days, will be summarized descriptively considering the following continuous variables:

cc1 [REDACTED]  
cc2 [REDACTED]  
cc3 [REDACTED]  
cc4 [REDACTED]

and the following qualitative variables:

cc1 [REDACTED]  
cc2 [REDACTED].

The results of MRI in the 2 years prior to study enrollment will be summarized descriptively with respect to the above continuous variables **cc1** [REDACTED]

[REDACTED] For patients who were diagnosed with MS less than 24 months prior to written informed consent, MRI results since diagnosis will be summarized.

### **Baseline Data on Previous MS DMD Use and Past Treatment Adherence**

DMD treatments received in the 2 years prior to study enrollment (including medication doses and routes of administration, start dates, stop dates, and reasons for discontinuation) will be collected. A listing with the above characteristics and the date of diagnosis will be presented.

For each previous DMD received for MS during the last 2 years, the corresponding number and percentage of patients who received it will be presented. The corresponding reasons (number and percentage) for discontinuation will also be reported.

The number of previous DMDs received for MS (a) during the last 2 years and (b) in total will be summarized descriptively, considering them as continuous variables.

DMD treatments received since diagnosis will be summarized for patients diagnosed with MS at least 12 months but less than 24 months prior to written informed consent.

Past treatment adherence data will be collected before the first dose of cladribine tablets is taken. Data collected at Baseline through the modified version of the MS-TAQ for once- or twice-daily oral dosing to assess adherence during the last previous oral DMD treatment or collected at Baseline through the modified version of the MS-TAQ to assess adherence during the last previous infused DMD treatment will be summarized descriptively.

